11.3.6. Action Taken Regarding the Investigational Drug Product

The Investigator will provide information regarding the action taken with respect to the IP in response to the AE.

11.3.7. Expectedness of an Adverse Event

The expectedness of all AEs will be determined according to the most recent version of the Investigator's Brochure for eteplirsen.

11.3.8. Suspected Unexpected Serious Adverse Reactions (SUSAR)

Suspected unexpected serious adverse reactions (SUSARs) will be handled by appropriate personnel at the Sponsor or designee and reported within the required timelines in an unblinded fashion to regulatory authorities and institutional review boards/independent ethics committees

(IRBs/IECs) per the requirements of the concerned competent bodies. SUSARs will also be reported to study Investigators.

11.4. Recording Adverse Events

All AEs/SAEs experienced from the time of informed consent/assent to the last follow-up will be recorded within each patient's CRF. Information should include: a concise description of the event; date and time of event onset and resolution; determination of seriousness, severity, corrective treatment, outcome, and relationship to IP or study procedure or underlying disease; and any action taken will be recorded. Resolution occurs when the patient has returned to his Baseline state of health or further improvement or worsening of the event is not expected.

Whenever possible, a diagnosis will be recorded as an AE, rather than symptoms or isolated laboratory abnormalities related to that diagnosis. Several symptoms or laboratory results that are related to the same diagnosis can thus be part of the same AE. A medical or surgical procedure is not an AE; rather the condition leading to the procedure should be recorded as the AE. Similarly, death is not an AE, but is rather the outcome of the AE(s) that resulted in death. If the AE(s) leading to death are not known, then death must be reported as an AE. All AEs will be followed until the resolution of AE, completion of the patient's study participation, or study termination, whichever occurs first. SAEs will be followed until resolution or until the condition stabilizes or returns to Baseline status.

11.5. Reporting Serious Adverse Events

It is the responsibility of the Investigator that reporting is done adequately. In order to meet Regulatory reporting timelines, the study site is obligated to report any SAE(s) to the Sponsor or designee immediately and no later than 24 hours after receiving information of an event that meets at least one of the criteria for seriousness as defined in Section 11.2.2. Refer to the SAE Reporting Plan for further details on the transmission of SAE Reports.

11.6. Special Situations

11.6.1. Overdose

An overdose is defined as administration of a dose above 50 mg/kg. An overdose is not an AE. An overdose will be reported even if it does not result in an AE. An overdose will be recorded on the appropriate form and sent to the Sponsor or designee within 24 hours.

11.6.2. Death

Death is an outcome of an event. All causes of death are SAEs. In the event of death, every effort should be made to obtain a death certificate and if possible, an autopsy report. If the cause of death is unknown, death will be recorded as the event.

11.6.3. Responsibilities of the Investigator

- The responsibilities of the Investigator and his or her staff include the following:
- Monitor and record all AEs
- Determine seriousness, severity, and relationship to IP and/or study procedure and/or underlying disease
- Determination of the onset and end date of each event
- Provide initial report on all SAEs within 24 hours of knowledge to the Sponsor or designee
- Provide follow-up information on SAE in a timely and proactive manner
- Respond to queries regarding AEs and SAEs in a timely manner
- Ensure source documentation for all AEs are accurate and complete

11.6.4. Responsibilities of the Sponsor

The responsibilities of the study Sponsor (Sarepta Therapeutics, Inc.) include the following:

- Training of Investigator and site staff on AE/SAE definitions, safety assessments, and site obligations related to safety monitoring and reporting of AE/SAEs
- Training with regard to the accurate and legal reporting of SAEs to all applicable regulatory bodies, IRBs/IECs, clinical trial sites, and other parties as appropriate and required within the regulated timing
- Ensuring accurate recording of AEs and SAEs
- Notification of expedited SAEs to sites
- Annual safety reporting to regulatory authorities and IRBs/IECs according to regional requirements

12. DATA COLLECTION, QUALITY ASSURANCE, AND MANAGEMENT

12.1. Recording of Data

Clinical data for this study will be captured in an electronic format. Electronic data capture (EDC) will be provided by a contract research organization. The Investigator, or personnel delegated by the Investigator, will perform primary data collection/perform assessments based on the protocol design and captured in source documentation. All required study information must be recorded on the appropriate CRF screens/forms using the CRF Completion Guidelines for the study. A CRF must be completed for each patient that is enrolled. The study monitor will conduct 100% source data verification to ensure maximum data integrity. All data must be carefully entered in a timely fashion to permit meaningful interpretation and study oversight.

12.2. Quality Assurance

The CRFs will be reviewed at regular intervals by a clinical monitor from the Sponsor or a representative of the Sponsor per the agreed upon Monitoring Plan against the source documentation for identification and clarification of any discrepancies. Automated and manual quality checks will be in place to identify discrepancies, such as missing data, protocol deviations, out-of-range data, other data inconsistencies and compliance. Requests for data clarification or correction will be documented as electronic queries within the CRF and for the Investigator or study coordinator to resolve. All changes to the CRFs will be tracked in an electronic audit trail. Site Study Files will be reviewed for compliance throughout the study.

Audits may be carried out by the Sponsor's representatives, and inspections may be performed by IRBs/IECs or regulatory authorities before, during, or after the study. The Investigator will allow and assist the Sponsor's representatives and any regulatory agency to have direct access to all study records, CRFs, patient medical records and other source documentation, IP dispensing records and IP storage area, study facilities, and any other source documentation.

The Investigator must make study files and data accessible to the study monitor, to other authorized representatives of the Sponsor, and to the appropriate regulatory authority inspectors such as the United States Food and Drug Administration (US FDA).

12.3. Retention of Study Documents

At study completion, all CRF data for an individual site will be copied onto a compact disc (CD) and provided to the Investigator for retention in the Study Files. The supporting Site Study Files must be retained by the Investigator for a period of 2 years following the date a marketing application is approved for the drug for the indication for which it is being investigated; or, if no application is to be filed, or if the application is not approved for such indication, until 2 years after the investigation is discontinued and regulatory authorities are notified.

However, these documents should be retained for a longer period, if required by the applicable regulatory requirements or by an agreement with the Sponsor. No study documents will be

destroyed or moved to a new location without prior written approval from the Sponsor. If the Investigator relocates, retires, or withdraws from the clinical study for any reason, all records that are required to be maintained for the study should be transferred to an agreed upon designee.

Patient records or other source data must be kept for the maximum period of time mandated by the hospital, institution, or private practice, but not less than 15 years.

If off-site archiving is used, all records should be retrieved and made available for review at the time of an audit or regulatory authority inspection.

12.4. Termination of Study or Study Site

If the Sponsor, the Investigator, the medical monitor, the study monitor, IRB/IEC, or appropriate regulatory officials discover conditions arising during the study that indicate the study should be halted or that the study center should be terminated, appropriate action may be taken after consultation among (at a minimum) the Sponsor, the Investigator, IRB/IEC and the medical monitor.

Conditions that may warrant termination of the study or an individual site include, but are not limited to, the following:

- The discovery of an unexpected, serious, or unacceptable risk to patients enrolled in the study
- A decision by the Sponsor to suspend or discontinue testing, evaluation, or development of the product
- Failure of the Investigator to enroll patients into the study at an acceptable rate
- Failure of the Investigator to comply with pertinent regulations of IRB/IEC or appropriate regulatory authorities
- Submission of knowingly false information from the research facility to the Sponsor, the study monitor, IRB/IEC or regulatory authority
- Insufficient adherence to protocol requirements consistent with 21 CFR 312 or the European Clinical Trial Directive 2001/20/EC

Study termination and follow-up will be performed in compliance with the conditions set forth in International Council on Harmonisation (ICH) E6 on Good Clinical Practice (GCP) as well as 21 CFR 312.56b and the European Clinical Trial Directive 2001/20/EC which require a Sponsor to ensure an Investigator's compliance with these requirements and to promptly secure a plan for compliance or discontinue shipments of the IP to the Investigator and end the Investigator's participation in the investigation.

13. STATISTICAL METHODS AND PLANNED ANALYSES

13.1. General Considerations

This section describes the rules, conventions, statistical analysis, and presentation of data for this study. Full details will be provided in the final Statistical Analysis Plan (SAP) for this study.

Revisions during the study may be made to accommodate protocol amendments and to make changes to adapt to unexpected issues in study execution that could affect planned analyses. Any revisions will be based on blinded review of the data. A formal SAP for the analysis and presentation of data from this study will be prepared and issued before database lock. The SAP will provide a more technical and detailed description of the proposed data analysis methods and procedures. Deviations from the statistical analyses outlined in this protocol will be included in this plan; any further modifications will be noted in the clinical study report (CSR). All statistical analyses will be performed by or under supervision of the Sponsor.

All available data will be included in data listings and tabulations. No imputation of values for missing data will be performed. Percentages of patients with AEs or laboratory abnormalities will be based on non-missing values.

[figure not shown]
All data collected in this study will be presented using summary tables and patient data listings. Summary statistics for raw and change from Baseline data of continuous variables will minimally include n, mean, standard deviation (SD), minimum, median, and maximum. For categorical variables, frequencies and percentages will be presented. Graphical displays will be provided as appropriate.

Endpoints will be assessed primarily using simple descriptive statistics and/or inferential statistics. Baseline will generally be defined for the treated group as the last available value before dosing, and the equivalent time point for the untreated control group.

13.2. Determination of Sample Size

DMD patients have consistently shown progressive decline in 6MWT data secondary to disease progression. The extent of decline has been shown to be affected by stride length and age (McDonald 2010a), and the use of steroids (Mazzone 2011). For example, in a natural history study that included patients with a broader range of ages and functional abilities, patients who were older than 7 years of age lost a mean of 42.3 meters (SD = 73.9 meters; N = 71) over the course of a year (Mazzone 2011). In another natural history study of 18 boys with Duchenne/Becker muscular dystrophy 4 to 12 years of age, patients lost a mean of 57 meters (SD =104 meters) over the course of approximately 1 year (McDonald 2010b); the distance lost was even greater (115 meters) in boys older than 7 years of age (n = 10). More recently, completed studies with the drug ataluren from PTC Therapeutics presented a decline of about 60 meters after 48 weeks in the 34 placebo-treated patients who were ≥7 years old who were on steroid for the duration of the study (McDonald 2013).

This study will enroll approximately 90 patients with Baseline 6MWT distance of 300 to 450 meters, including approximately 70 patients in the eteplirsen-treated group and

Additionally, approximately 20 patients (10 treated vs 10 untreated control) with Baseline 6MWT distance of >450 meters at Baseline will be enrolled.

13.3. Analysis Sets

Patients will be analyzed by treatment (eteplirsen 30 mg/kg/week versus untreated control). Three analysis populations will be considered:

Efficacy Set: All patients in treated and untreated control groups who have at least 1 post-Baseline functional assessment. The efficacy set for the primary efficacy analyses will be patients with baseline 6MWT distance of 300 to 450 meters, inclusive. If external control patients are included as a comparator of eteplirsen-treated group, the efficacy set may be expanded accordingly, with the primary efficacy set for the primary endpoint defined in the SAP.

Safety Set: Treated patients who are enrolled in the study and receive at least 1 dose of eteplirsen and untreated control patients who are enrolled in the study and have at least 1 post-Baseline safety assessment.

Pharmacokinetic Set: All patients in treated group who receive a full dose of IP at the visits where PK sampling is to be done and for whom there are adequate PK samples from which to estimate population PK parameters.

13.4. Protocol Deviations

A listing of protocol deviations will be provided. This deviation listing will be based on the blinded review of study data prior to locking the database and will include the nature of the deviation (e.g., inclusion/exclusion, prohibited therapies).

13.5. Disposition, Demographics, and Baseline Characteristics

The number and percentage of patients completing or prematurely discontinuing the study will be summarized by treatment group. Reasons for premature discontinuation will also be summarized.

Demographic characteristics including age (years), race, ethnicity, and Baseline characteristics including height (cm), weight (kg), body mass index (kg/m²), will be summarized by treatment group. Demographic data and Baseline characteristics will be presented in data listings.

13.6. Prior and Concomitant Medications and Physiotherapeutic Interventions

All prior and concomitant medications, as well as physiotherapeutic interventions, will be presented in data listings.

13.7. Medical History

Medical history will be presented in data listings.

13.8. Dosing and Compliance

The cumulative exposure to eteplirsen, total volume of drug administered (mL), total number of infusions received, and the cumulative amount of drug received will be summarized by dose group for all treated patients. Dosing information will be provided in a data listing.

13.9. Efficacy Analyses

All efficacy data will be summarized descriptively by visit and treatment group. Actual values and change from Baseline values will be summarized by time point and treatment.

The efficacy set for the primary efficacy analysis will be patients with a Baseline 6MWT distance of 300 to 450 meters, inclusive.

13.9.1. Efficacy Variables

13.9.1.1. Primary Efficacy Endpoint

• Change from Baseline to Week 96 in the 6MWT

13.9.1.2. Secondary Efficacy Endpoints

- Change from Baseline in dystrophin protein levels quantified by Western blot (treated patients only)
- Change from Baseline in dystrophin intensity levels determined by immunofluorescence (treated patients only)
- Ability to rise independently from the floor (without external support), as indicated by an NSAA subscore of "2" (without modification) or "1" (Gower's maneuver)
- Loss of ambulation (to be defined in the SAP),
- Change from Baseline in FVC % predicted
- Change from Baseline in NSAA total score

13.9.2. Analyses of Primary Efficacy Endpoint

The analysis of change from Baseline to Week 96 (the primary time point of interest) in the 6MWT will be based on a mixed model repeated measures (MMRM) analysis, with treatment group, time, time by treatment group interaction, Baseline 6MWT distance, and Baseline 6MWT distance by time interaction as fixed effects; and patient as a random effect. Additional baseline variables may be added as covariates in the SAP. A heterogeneous autoregressive (1) variance-covariance matrix will be used. Estimates for changes from Baseline at each time point in each treatment group and for treatment differences will be provided with 95% confidence intervals and descriptive p-values using appropriate contrasts from the model. Due to the potential difference in progression based on DMD genotype in the control group, notably those with deletions amenable to skipping exon 44, additional sensitivity analyses may be performed.

If there is strong evidence suggesting that data for any of these endpoints deviate from normal distribution, then an analysis of covariance (ANCOVA) for ranked data (Stokes 2000) will be utilized.

13.9.3. Analyses of Secondary Efficacy Endpoints

As muscle biopsies will be confined to the treated group, the analysis of the secondary endpoints of change from Baseline in the dystrophin protein levels by Western blot and dystrophin intensity levels determined by immunofluorescence will be based on a 1-sample permutation t-test. These analyses will be performed for patients in the treated group only.

The analysis of the secondary endpoints of time from Baseline to loss of the ability to rise independently (from supine to standing) and time to loss of ambulation will be analyzed using the Kaplan-Meier method. The analyses of the secondary efficacy endpoints of change from baseline in FVC% predicted and change from baseline in NSAA total score will be similar to the primary endpoint.

13.10. Safety Analyses

13.10.1. Safety Variables

The safety and tolerability of eteplirsen will be evaluated by:

- The type, frequency, severity, timing, and relationship to IP of AEs, SAEs, and AEs leading to discontinuation. Adverse events will be coded using Medical Dictionary for Regulatory Activities (MedDRA) and will be reported by primary system organ class (SOC) and preferred term (PT)
- Adverse events will be classified as treatment-emergent (TEAE) and non-emergent. TEAEs are those AEs that develop or worsen during the on-treatment period. An AE will be considered treatment emergent if it begins on or after dosing with IP and up until 30 days after the last administration of IP. Non-emergent events are those that develop during the pre-treatment period

- Clinical laboratory testing including chemistry, hematology, coagulation, and urinalysis
- Vital signs
- Physical examinations
- ECG
- ECHO: EF and FS

13.10.2. Safety Analysis

Safety analyses will be descriptive in nature. When appropriate, patients who have been treated previously with drisapersen will be summarized separately within the treatment group. Summary statistics for each parameter at a specific visit, as well as the change from Baseline to that visit, will also be displayed. All safety data will be presented in the data listings.

13.10.2.1. Adverse Events

For treated patients, only TEAEs will be summarized. Non-treatment emergent events will be recorded in data listings. For all AE tables, the number and percent of patients reporting AEs (grouped by MedDRA SOC and PT) will be summarized by treatment group. In general, tables will have events categorized into all TEAEs and treatment-related TEAEs.

As untreated patients (control group) will have no TEAEs, AEs collected post-qualification for the study will be summarized similarly to treated patients' TEAEs. All captured AEs for this control group will be listed.

Multiple occurrences of the same AE (at the PT level) in the same patient will be counted only once in frequency tables. If a patient experiences multiple episodes of the same event with different relationship/severity, the event with the strongest relationship and maximum severity to IP will be used to summarize AEs by relationship and severity. Treatment-related TEAEs will be defined as those that the Investigator considers possibly/probably or definitely related to the IP.

The following summary tables will be produced:

- TEAEs
- TEAEs by severity
- Treatment-related TEAEs
- Treatment-related TEAEs by severity
- SAEs

In addition, all SAEs, regardless of their treatment-emergent status will be summarized by SOC and PT.

The following listings will be produced:

- Non-treatment emergent AEs
- All TEAEs
- AEs leading to discontinuation
- SAEs

13.10.2.2. Physical Examination and Vital Signs

Vital signs, weight, and height will be presented by treatment group and visit, summarizing the actual values and change from Baseline to each visit for each parameter using descriptive statistics. Frequency tables of predefined change abnormal in vital sign values will be generated.

Results from physical examinations will be presented in patient data listings.

13.10.2.3. Clinical Laboratory Tests

Clinical chemistry, hematology, coagulation, and urinalysis will be presented by treatment group and visit, summarizing the actual values and change from Baseline to each visit for each parameter using descriptive statistics for each continuous, and frequency tables for each discrete parameter. Frequency tables of predefined change abnormal of select laboratory parameter values will be generated.

13.10.2.4. Electrocardiograms

The actual value and change from Baseline to each visit will be presented by treatment group and visit, summarizing the actual values and change from Baseline to each visit for each parameter using descriptive statistics. Shift and frequency tables of predefined change abnormal of select ECG parameter values will be generated.

13.10.2.5. Echocardiograms

The actual value and change from Baseline to each visit will be summarized by treatment group for each ECHO for EF and FS.

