5. INTRODUCTION AND RATIONALE

5.1. Background of Duchenne Muscular Dystrophy

Duchenne muscular dystrophy (DMD) is a rare (estimated incidence of 1 in 3,500-5000 live births; CDC 2009; Emery 1991), degenerative, X-linked recessive genetic disorder caused by mutations in the dystrophin gene. In DMD, mutations in the dystrophin gene disrupt the open-reading frame, resulting in an absence of functional dystrophin, a critically important part of the protein complex that connects the cytoskeletal actin of a muscle fiber to the extracellular matrix. In the absence of dystrophin, the stress of repeated muscle contraction causes cellular degeneration, regeneration, and inflammation, and, over time, myonecrosis.

The progression of DMD follows a highly predictable course. Significant motor deficits may be present during the first year of life, but diagnosis is usually made between the ages of 3 to 5 years when toddlers begin to show functional symptoms (e.g., waddling gait, toe walking, and difficulty climbing stairs). Over time, ambulation becomes increasingly abnormal, and by 8 years of age, most patients lose the ability to rise from the floor and climb stairs, and often fall while walking. By 10 to 14 years of age, most lose the ability to walk. Upper limb, cardiac, and diaphragmatic muscles progressively weaken during adolescence. Historically, patients died from respiratory or cardiac failure in their late teens or early 20s (Brooke 1989, Eagle 2002). Recent research suggests that use of ventilation support and steroids may increase life span by several years; however, DMD still has a mortality rate of 100% (Kohler 2009).

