4.4.2 Final Analysis

A final analysis of safety and efficacy will be conducted once the last patient completes the entire study and the resulting database is cleaned, quality assured, locked, and unblinded. All statistical analyses will be performed by or under the supervision of the Sponsor. All available data will be included in data listings and tabulations. Due to the small population size and large dropout rate of the untreated control group, only descriptive summaries will be presented. An external control dataset will be identified and used to evaluate the effect of eteplirsen treatment. The statistical methods for the identification and use of the external control dataset will be presented in a supplemental SAP.

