7.9.4 Electrocardiograms and Echocardiograms

Electrocardiogram (ECG) and echocardiogram (ECHO) assessments will be summarized by treatment group using descriptive statistics. For each ECG and ECHO parameter, the baseline and final observations will be presented by treatment group. Additionally, the largest change from baseline QT interval corrected for heart rate, QRS, and PR intervals, the highest value of QT and the largest absolute change for heart rate will be summarized. Descriptive statistics will be calculated for the observed values as well as the change from baseline values.

A table of frequencies of ECG and ECHO abnormalities of interest that occur after baseline as defined in [Appendix Table 5](#) will be generated by treatment. The number and

percentage of patients experiencing the abnormality as well as the total number of abnormalities will be presented. All ECGs and ECHOs with an abnormality will be listed.

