8. CHANGES IN PLANNED ANALYSES

8.1. Changes from Protocol-Planned Analyses

The following changes were made compared to the protocol-planned analyses:

- Comparisons between the eteplirsen-treated group and the untreated control group will not be performed due to the expected very small number of patients in the untreated control group and the differences in the populations between the treated and untreated groups. No hypothesis test, no p-value and no inferential statistics will be made for comparison of eteplirsen treated patients and untreated patients
- CCI [REDACTED]
- The observed values and changes from baseline for clinical laboratory assessments, vital signs and ECG will only be summarized for baseline, the last visit (final observation) and the highest/lowest values. All clinical laboratory assessments, vital signs and ECG results by visit will be in data listing.
- Renamed “predefined change abnormal” to “predefined markedly abnormal” for clinical laboratory tests and other safety endpoints.
- CCI [REDACTED]

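### The protocol plans EF and FS change at every ECHO visit; the SAP summarises only baseline and final observation, and its readable change log does not mention ECHO

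*Protocol*

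**What the plan says.** EF and FS are named safety measures in Protocol 7.3.2 and SAP 3.2. Protocol 13.10.2.5 sets out their summary: "The actual value and change from Baseline to each visit will be summarized by treatment group for each ECHO for EF and FS".

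SAP 7.9.4 is different: "For each ECG and ECHO parameter, the baseline and final observations will be presented by treatment group". Descriptive statistics cover observed values and change from baseline. The extra extreme-value summaries in that section concern ECG quantities (QT, corrected QT, QRS, PR and heart rate), not EF or FS. The section also plans an abnormality table, "A table of frequencies of ECG and ECHO abnormalities of interest that occur after baseline as defined in" Appendix Table 5 (LVEF below 55%, FS below 29%), and a listing of abnormal ECGs and ECHOs.

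SAP 8.1 declares a reduction of by-visit summaries. The observed values and changes for "clinical laboratory assessments, vital signs and ECG will only be summarized for baseline, the last visit (final observation) and the highest/lowest values". It then says where the by-visit data go: "All clinical laboratory assessments, vital signs and ECG results by visit will be in data listing". Neither sentence names ECHO. Two other bullets in 8.1 are redacted.

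On follow-up, SAP 4.4.2 says: "Due to the small population size and large dropout rate of the untreated control group, only descriptive summaries will be presented". Protocol Table 4 and Section 10.2.11 list no ECHO in the safety extension.

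**The concern.** A protocol-planned summary of a cardiac safety measure has been reduced, and the place where such reductions are declared does not, as far as it can be read, declare this one. The by-visit listing offered in 8.1 as a replacement for the other measures does not name ECHO either.

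The reduction matters because a final observation is not a fixed time point. A treated boy who completes has his last ECHO at about Week 96. A boy who leaves has his at an earlier scheduled visit or at early termination. The SAP says that leaving was common among controls. The protocol describes the disease as one in which "Upper limb, cardiac, and diaphragmatic muscles progressively weaken during adolescence", so elapsed time may itself change EF and FS. A reader who sets the two columns side by side would then be looking at different lengths of follow-up, without n by visit or the week of the last ECHO to show it.

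**Working it through.** **Step 1. The texts side by side**

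| Item | Protocol 13.10.2.5 | SAP 7.9.4 | SAP 8.1, readable text |
|---|---|---|---|
| EF/FS value and change | Each visit, by group | Baseline and final observation, by group | ECHO not named |
| Laboratory, vital signs, ECG | Not covered here | ECG: baseline, final and extremes | Reduction declared |
| By-visit listing | Protocol 13.10.2: all safety data listed | Abnormal ECHOs listed | Promised for laboratory, vital signs and ECG |

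The EF and FS value and change summaries differ between the documents, and no readable text explains it.

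**Step 2. When the final ECHO falls**

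The schedule tables (Protocol Tables 2, 3 and 5) place post-baseline ECHO at Weeks 24, 48, 72 and 96 or early termination. The treated row for Weeks 49 to 96 is broken in the text available; its two entries are read here as Weeks 72 and 96, the two Hub Site visits in that table. Protocol 10.2.7, covering Weeks 12 to 72, restricts ECHO to Week 24. These passages conflict. Under either, a completer's last ECHO is at about Week 96, because Section 10.2.10 includes one there, and a dropout's is usually earlier.

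**Step 3. Illustration of the timing gap**

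The plan gives no figure to reproduce: no dropout rate, dropout timing or EF slope is stated. All of the following inputs are assumptions:

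- Treated dropout of 5% or 10%, with mean last ECHO at Week 48.
- Control dropout of 30%, 50% or 70%.
- Control dropouts' last ECHO all at Week 24, spread evenly over Weeks 24, 48 and 72 (mean 48), or all at Week 72.
- EF decline of 1 to 2 points per year, equal in both arms.

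Mean final week = (1 − d) × 96 + d × m, where d is the dropout proportion and m the dropouts' mean last ECHO week.

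- Treated: 0.95 × 96 + 0.05 × 48 = 93.6, or 0.90 × 96 + 0.10 × 48 = 91.2.
- Controls, longest follow-up: 0.70 × 96 + 0.30 × 72 = 88.8.
- Controls, shortest follow-up: 0.30 × 96 + 0.70 × 24 = 45.6.

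Gap in weeks (treated minus control), shown for 5% / 10% treated dropout:

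| Control dropout | Last ECHO Week 24 | Spread evenly | Last ECHO Week 72 |
|---|---|---|---|
| 30% | 19.2 / 16.8 | 12.0 / 9.6 | 4.8 / 2.4 |
| 50% | 33.6 / 31.2 | 21.6 / 19.2 | 9.6 / 7.2 |
| 70% | 48.0 / 45.6 | 31.2 / 28.8 | 14.4 / 12.0 |

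**Step 4. Conversion to EF**

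Shift = (gap ÷ 52) × annual decline.

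- Smallest: 2.4 ÷ 52 × 1 = 0.05 points.
- Largest: 48 ÷ 52 × 2 = 1.85 points.
- Middle case (50% dropout, spread evenly): 19.2 ÷ 52 × 1 = 0.37 up to 21.6 ÷ 52 × 2 = 0.83 points.

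The shift is zero if EF does not fall over the period, or if the arms drop out alike. In a by-visit table the nominal timing gap is zero by construction.

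**The case against.** **No between-arm comparison is intended.** SAP 6.3 and 8.1 rule out comparisons of treated and untreated patients, and safety is descriptive throughout. This stands: no test, estimate or decision rule is affected. But the by-group columns will still be printed next to each other, and they will be read.

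**ECHO is not reduced to two numbers.** The SAP also tabulates and lists post-baseline abnormalities. This stands, and limits the point to the value and change summaries. The table is only a partial substitute. Entry excludes LVEF below 50%, while the flag is below 55%, so a boy entering at 50 to 54% could be flagged without any change. Boys followed longer also have more ECHOs on which to be flagged.

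**The data remain available.** A reader might infer that the cardiac time course is lost. The documents do not support that: Protocol 13.10.2 promises that all safety data will be listed, and SAP 4.4.2 promises that all available data will be listed and tabulated. What is missing is a summary table. The narrower listing rules in SAP 7.9.4 and 8.1 leave the full ECHO listing unclear rather than excluded.

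**The change may be declared, or may not be a change.** Two bullets in SAP 8.1 are redacted, so non-declaration cannot be proved. SAP 7.9.4 also does not say that baseline and final are the only ECHO summaries; it could be read as leaving the protocol table in force. Either reading is cured by one explicit sentence.

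**The fix has limits.** A by-visit table replaces unequal timing with selective attrition. With about 30 planned controls (20 + 10), an assumed 50 to 70% dropout leaves 15 to 9 at Week 96. That is correct, but such a table shows n at each visit, whereas a final-observation table hides it.

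**Conclusion.** The point holds as a discrepancy between protocol and SAP in a descriptive cardiac safety summary, with a plausible consequence for interpretation. The by-visit EF and FS summaries in the protocol are not carried into SAP 7.9.4, and the readable text of 8.1 does not declare their removal. Final observations would fall at different times in the two arms if, as the SAP indicates, dropout is concentrated among controls.

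A reader might go further and infer that treated boys will show a larger EF fall with no drug effect. The documents do not establish this. That direction requires EF to decline over the study period. The protocol describes cardiac weakening in adolescence but gives no EF slope, and the trial enrols from age 7. Nor can a definite size be stated: 0.05 to 1.85 EF points is an illustration in which the dropout rates, dropout timing and annual decline are all assumed, and its lower end is negligible. The discrepancy does not depend on those assumptions. It is worth correcting because the correction is cheap.

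**What to change.** 1. In SAP 7.9.4, restore EF and FS observed value and change from Baseline by scheduled ECHO visit and arm, with n at each visit. Show early-termination ECHOs on a separate line.
2. Keep final observation as a supplement. Define it and report its study week by arm.
3. List all ECHO results by visit, not only the abnormal ones.
4. Reconcile Protocol 10.2.7, which restricts ECHO to Week 24, with the schedule tables, so that the visits in the new table are defined.
5. If the sponsor prefers not to restore the table, name ECHO in the SAP 8.1 declaration with a reason, and still carry out items 2 to 4.

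The cost is one by-visit table for two parameters and one listing, both from data already collected, plus a short clarification of the visit text. The table should carry a note that boys remaining at later visits are a selected group and that the summary is descriptive.
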